Preliminary Work. In 2011, we completed focus groups with Baltimore public housing residents exploring perceptions of health and community. Potential facilitators of behavior change included support from family members and cohesion among neighbors in housing courts; however, individuals reported limited access to fresh foods and safe areas for recreation. We completed a cross-sectional survey characterizing the personal diet, eating, and exercise habits and the perceptions of these habits among the social networks of over 350 adults living in Latrobe Homes and Gilmore Homes public housing developments in September 2015. We captured data on perceptions of the built environment along with observer ratings of the community environment and geographic information system (GIS) data. While analyses are ongoing, preliminary results show that over 50% are obese ($BMI \geq 30$ kg/m²) and proportion with self-reported diabetes mellitus is 20%. We found that the median added sugar intake was 21.1 tsp per day as compared to the 6 to 9 tsp per day recommended by the American Heart Association. In multivariate models, individuals who perceived a greater proportion of their social networks drank sugar-sweetened beverages or ate sweets daily had significantly higher added sugar intake. We used this prior study to inform the development of a social network-built environment intervention to reduce added sugar intake among public housing residents, which will be tested in this pilot study.

The study team has prior experience conducting focus groups and a cross-sectional survey among public housing residents in Baltimore City, and has a long-term relationship with the Housing Authority of Baltimore City to conduct this research.

4. Study Procedures

a. Study design

We will conduct a 6-month non-randomized trial of the social network intervention described below. This will be a single arm trial in which we compare the outcomes of interest pre- and post- intervention. We have elected to use a pre-post design in this pilot study, given the preliminary nature of this work. We will adapt an HIV risk reduction social network intervention to create a new social network intervention targeting reduction in intake of added sugars. Our primary outcomes will be to test the acceptability and feasibility of the intervention and its components as well as estimate the likely effect of the intervention.

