In the intervention, individuals will be recruited and trained to be “Peer Educators” who will participate in group sessions and then communicate this information with members of their social network (“Sidekick”) and work to make changes to reduce intake of added sugars together. Given the frequent intake of sugar-sweetened beverages (SSB) in this population, the intervention will focus on reducing added sugar intake through the reduced consumption of SSB. Peer Educators will participate in 6 core group sessions over a 6-week period as well as 3 additional booster sessions over the subsequent 3 months after completing the core curriculum. All sessions will be delivered by a facilitator and assistant facilitator using a guide (Appendix A). All groups will be held in a room in each public housing development’s administrative building. Participants will receive a healthy meal or snack during each group session. We anticipate each group will last approximately 90 minutes.

We will recruit participants from Latrobe Homes and Gilmor Homes. We will recruit a total of 24 overweight Peer Educators along with 24 of their social network members (12 Peer Educators from Latrobe and 12 Peer Educators from Gilmor). We will require that both Peer Educators and Sidekicks consume sugar-sweetened beverages at least twice a day. We will require that the Peer Educator and Sidekicks have had in person contact at least once during the past month, which suggests a more significant relationship. We will not require Sidekicks to live in the housing development, as many individuals’ social networks extend beyond their immediate neighborhood.

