Peer Educators will give their potential Sidekicks an invitation (Appendix D) describing the study, the roles of Peer Educators and Sidekicks, and directions on how to contact study staff for screening. We will use a telephone script to handle all calls generated from this letter (Appendix E). To address privacy issues during recruitment, all participants who are contacted or approached for recruitment will be assured that the research staff at Johns Hopkins will be the only ones to see their information, and that the information we collected will be kept private and be used only for the research study we are discussing. If the potential participant chooses not to enroll in the study or does not qualify to be in the study as a Sidekick, then his/her information will be destroyed.

Peer Educators and Sidekicks will complete a baseline study visit for data collection, along with 3- and 6-month follow up visits for data collection (Appendices F-H). At baseline and 6-month follow up, data collection will include a survey that has individual-level questions, biometric measurements, and an egocentric social network inventory.

□ Individual-level questions:

- Demographics including age, gender, race/ethnicity, and address
- Dietary content with brief food frequency questionnaire using the 5-Factor NHIS screener
- Modified 3-Factor Eating Questionnaire R18 □ Biometric measurements:
- Height using rafter square method where respondents remove their shoes and stand on a smooth surface with their heels and shoulders against a wall. Interviewer will then place a rafter square on the respondent's head, mark the height on a wall, and then measure it in inches (to the nearest quarter inch) using a tape measure.
- Weight on portable scale
- Blood pressure via automated sphygmomanometer □ Egocentric social network inventory:
- At baseline, each study participant will begin by listing 10 people he/she knows and has had contact with sometime during the past year. Only first names or initials of these alters will be recorded, so they are not identifiable to the research team and will not be sought out as research subjects. The ego will then answer questions regarding the nature of his/her relationship with these alters and list characteristics of each alter including demographics, socioeconomic status, body

size via pictogram, as well as lifestyle behaviors. Finally, we will assess for ties among these alters.

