- At 3- and 6-months, we will repeat questions on body size via pictogram, lifestyle behaviors, and ties among these alters of the 10 original alters named at baseline. We will also ask each study participant to list up to 5 additional people who have become a part of their social network over the last 3 and 6 months, respectively. The ego will then answer questions regarding the natures of his/her relationship with these alters and list characteristics of each alter including demographics, socioeconomic status, body size via pictogram, as well as lifestyle behaviors.

At 6 months, we will also ask questions regarding satisfaction with the intervention. At 3 months, an abbreviated survey will be conducted that includes only individual-level questions, biometric measurements, and satisfaction with the intervention. Study visits will be held either in the administrative building of the public housing developments or during home visits based on participant preference. Two data collectors will be present during surveys administered in the respondent's home. The survey will be administered in-person by trained research assistants. During the intervention, we will also collect sheets on which the Peer Educators and Sidekicks track their SSB intake (Appendix N).

Informed consent will be obtained from each participant during the baseline study visit for data collection. In particular, residents will be advised of the voluntary and confidential nature of participation. Residents will be asked questions about the study procedures to test their understanding and will be given materials, written at <5th grade level, to read and take home. They will also be provided the contact information of the principal investigator. We will emphasize that their participation in the study will not affect their clinical care.

All survey responses will be collected on password protected laptop computers and entered into the EgoNet software. EgoNet facilitates the collection of survey and egocentric social network data. The data is immediately stored onto the laptop's hard drive. At the end of each day, all data will be transferred to a secure network share drive on the password protected desktop computer in a study investigator's office ([name]). Once successful download is confirmed, the data will be erased from the laptop computer. Data will not be stored on servers external to the institution.

- b. Study duration and number of study visits required of research participants.

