Study duration will be 6 months. Peer Educators will be required to attend 6 core sessions and 3 booster sessions for the intervention. Peer Educators and Sidekicks will complete a baseline study visit for data collection, along with 3- and 6-month follow up visits for data collection. Study visits will be held either in the administrative building of the public housing developments or during home visits based on participant preference.
- c. Blinding
Not applicable
- d. Justification of why participants will not receive routine care or will have current therapy stopped.

Not applicable

- e. Justification for inclusion of a placebo or non-treatment group.

Not applicable

- f. Definition of treatment failure or participant removal criteria.

Not applicable

- g. Description of what happens to participants receiving therapy when study ends or if a participant's participation in the study ends prematurely. Not applicable

5. Inclusion/Exclusion Criteria

For Peer Educators to participate in the pilot, one of their social network members ("Sidekicks") who consume foods with added sugars daily must also enroll. Peer Educators and Sidekicks must be at least 18 years old and consume sugar-sweetened beverages at least twice daily. Peer Educators must have a BMI ≥ 25 kg/m².

We will exclude subjects with any underlying medical conditions that could seriously reduce their life expectancy, their ability to participate in the trial, or for which dietary change may be contraindicated and/or require medical supervision by a physician such as medication-dependent diabetes mellitus, cancer or malignant tumor, lung disease requiring supplemental oxygen, dementia or cognitive impairment, angina, or diagnosis in the last 12 months of myocardial infarction, congestive heart failure, transient ischemic attack or stroke, liver disease or kidney disease. We will also exclude women who are pregnant or breastfeeding. Only one person per household will be eligible to be a Peer Educator, and additional eligible household members can participate as a Sidekick.

6. Drugs/ Substances/ Devices

Not applicable

7. Study Statistics

- a. Primary outcome variables.

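### Does one baseline value, in people selected on sugary-drink intake, call for a second measurement before the sessions start?

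*Combined protocol and SAP*

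**What the plan says.** Section 4a describes a six-month single-arm trial that compares outcomes before and after the intervention, and justifies this by the early stage of the work. The primary outcomes cover acceptability and feasibility "as well as estimate the likely effect of the intervention".

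On entry, Section 4a states: "We will require that both Peer Educators and Sidekicks consume sugar-sweetened beverages at least twice a day". Section 5 repeats that both roles must "consume sugar-sweetened beverages at least twice daily". The invitation that a Peer Educator hands to a Sidekick gives "directions on how to contact study staff for screening", and staff handle those calls with a telephone script. Peer Educators are screened with a script by telephone or at the door.

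Measurement comes afterwards: "Peer Educators and Sidekicks will complete a baseline study visit for data collection", with follow-up at 3 and 6 months. The instrument is listed as "Dietary content with brief food frequency questionnaire using the 5-Factor NHIS screener". On mode, the plan says: "The survey will be administered in-person by trained research assistants". Self-monitoring is added while the sessions run: "we will also collect sheets on which the Peer Educators and Sidekicks track their SSB intake".

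Section 7a makes change in Sidekicks' added sugars the effect outcome. It gives a detectable reduction of 16.1 tsp/day with 24 people, SD 19, two-sided 5% and 80% power. Section 7c uses a paired t-test, or a Wilcoxon signed-rank test if the data are not normal. No repeat measurement before the first session is planned.

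**The concern.** People chosen because they report high intake tend to report less later, even if nothing has changed. Without a control arm, that fall cannot be told apart from an effect. The whole before side of the comparison is one brief self-report per person, so its random error passes straight into the change score.

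At stake is the effect estimate, one of the plan's primary outcomes, in 24 Sidekicks. It could be too large, and it is less precise than it might be. A short repeat of the added-sugar items before the first core session, averaged with the baseline value, looks like an inexpensive remedy. Feasibility and acceptability outcomes would not be affected either way.

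**Working it through.** **Inputs.** From Section 7a: n = 24, SD 19, two-sided 5%, 80% power, detectable change 16.1. Not in the documents, so assumed: the correlation between two pre-session values (r_bb), the correlation between baseline and 6 months (r_b6), the correlations of the screen with later values, and the share of people who pass the screen. Section 7c does not name the after visit; 6 months is taken here. The screening scripts are appendices that are not shown; the drink question is assumed to be asked there.

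**1. The plan's own figure.** SD of change = 19 × √(2 − 2·r_b6). With r_b6 = 0 this is 26.87. The exact paired t calculation (23 df) then gives 16.05, and power at 16.1 is 80.3%. So the stated figure reproduces if the two visits are treated as uncorrelated. With r_b6 = 0.5 the SD is 19.00 and the detectable change is 11.35.

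**2. Precision from a second value.** With the mean of two pre-session values, SD of change = 19 × √((1 + r_bb)/2 + 1 − 2·r_b6). Example at r_bb = 0.7, r_b6 = 0: 19 × √1.85 = 25.84, against 26.87, a fall of 3.8%; equivalent n = 24 × 2/1.85 = 25.9.

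| r_bb | r_b6 | Detectable change, one → two values | Fall in SD | Equivalent n |
|---|---|---|---|---|
| 0 | 0 | 16.05 → 13.90 | 13.4% | 32.0 |
| 0.5 | 0 | 16.05 → 15.01 | 6.5% | 27.4 |
| 0.7 | 0 | 16.05 → 15.43 | 3.8% | 25.9 |
| 0.9 | 0 | 16.05 → 15.84 | 1.3% | 24.6 |
| 0.5 | 0.5 | 11.35 → 9.83 | 13.4% | 32.0 |
| 0.7 | 0.5 | 11.35 → 10.46 | 7.8% | 28.2 |
| 0.8 | 0.5 | 11.35 → 10.76 | 5.1% | 26.7 |
| 0.9 | 0.5 | 11.35 → 11.06 | 2.5% | 25.3 |

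The 13.4% end requires two pre-session reports to agree with each other no better than either agrees with the 6-month report. If reports taken close together correlate 0.8 to 0.9, the gain is about 1% to 5%.

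**3. Possible regression to the mean.** Under no effect and a normal model, spurious fall = 19 × λ × (screen–baseline correlation − screen–6-month correlation), where λ = φ(z)/p and p is the share who qualify. Regression between screen and baseline is over before the baseline value is taken and does not enter.

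| Share qualifying | λ | Gap 0 | Gap 0.1 | Gap 0.2 | Gap 0.3 |
|---|---|---|---|---|---|
| 30% | 1.159 | 0 | 2.2 | 4.4 | 6.6 |
| 50% | 0.798 | 0 | 1.5 | 3.0 | 4.5 |
| 80% | 0.350 | 0 | 0.7 | 1.3 | 2.0 |

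Nothing in the documents says which cell applies.

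**4. What the second value does to drift.** Take 50% qualifying, gap 0.2, r_bb = 0.7 and r_b6 = 0.5. Root mean squared error (RMSE) = √(drift² + SD²/24). With one value: √(3.03² + 19²/24) = 4.92.

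| Situation | Drift | RMSE | Chance of a significant fall, no effect |
|---|---|---|---|
| One value | 3.03 | 4.92 | 11.3% |
| Two values, regression over by the second | 1.52 | 3.88 | 6.0% |
| Two values, half over | 2.27 | 4.24 | 8.8% |
| Two values, none over | 3.03 | 4.69 | 12.6% |

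In the last row the false-positive chance rises, because the test is sharper and the drift is unchanged. With no regression, RMSE goes from 3.88 to 3.58.

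**5. Value as a check on drift.** The change from first to second pre-session value has SD 19 × √(2 − 1.4) = 14.72 at correlation 0.7. Its 95% half-width is 6.2 tsp/day with 24 people, wider than every drift in step 3 except the most extreme. A flat result would not exclude regression.

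**6. Cost.** Up to 24 extra Sidekick contacts in person. Sections 4a and 8b require two data collectors for home interviews, and 8b requires a private room or screened booth elsewhere. Twelve Peer Educators per development would need private interviews on arrival at their first session. At the 25-dollar rate of the 3-month visit (Section 10), payments alone are 24 × 25 = 600 dollars for Sidekicks or 48 × 25 = 1,200 for all; staff time is extra.

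**The case for a change.** The best argument for acting is that pre-intervention data cannot be collected once the sessions have begun. Averaging two values improves precision whenever they are less than perfectly correlated, with no need for normality or for any regression to the mean. RMSE falls in every scenario in step 4. The repeat covers only part of a short questionnaire, and the plan already runs an abbreviated survey at 3 months.

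The direction of the precision gain stands. Three things weaken the case:

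- The gain may be as small as 1%. Raising it means spacing the two reports so that their recall periods do not overlap. The documents give neither the screener's recall period nor the interval from baseline to first session, so spacing could delay the start at each development.
- The reduction in bias is between none and half of an amount that may be zero.
- Sidekicks learn what the study is about from the invitation. Any real cut in intake before the first session would be averaged into the starting value and dilute the estimate, which the calculations above leave out.

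A second value would also leave untouched any time trend after the first session, the effect of the tracking sheets, and a wish to please at follow-up.

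**Conclusion.** No change follows; a single baseline is a fair trade-off for this pilot. No rule or figure in the plan is shown to be wrong, and its 16.1 tsp/day reproduces at 16.05. Screening is already separate from the baseline measurement, so only transient error common to both can bias the estimate. That bias is 0 to 6.6 tsp/day over the assumed range (30% to 80% qualifying, correlation gap 0 to 0.3, normal model, SD 19), and the documents cannot narrow it.

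A second pre-session value would lower the SD of change by about 1% to 13%, worth about 25 to 32 Sidekicks instead of 24. It would remove at most half of any drift, at the cost of extra contacts and perhaps a later start. Reasonable statisticians would differ on whether that is worth doing.

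The limits on causal reading come from the single-arm pre-post design, which Section 4a discloses and justifies. An analyst can report the result as a within-person change with a 95% confidence interval, without crediting all of it to the intervention. That wording alters no result and needs no amendment.

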Our feasibility outcomes will include recruitment and retention rates, as well as program attendance. Our acceptability outcomes will include participant satisfaction with the intervention and willingness to recommend that a friend participate as a Peer Educator. Our effect outcome will be change in intake in added sugars among Sidekicks using the relevant elements in the NHIS 5-factor screener. With a sample size of 24, the minimal detectable intervention effect is reduction of added sugar intake by 16.1 tsp per day (assuming a type I error of $\alpha=0.05$ (two-tailed), 80% power, and assuming SD of outcome of 19 based on our prior survey). Of note, a 12 oz can of soda has approximately 10 teaspoons of added sugars and a 20 oz bottle has approximately 17 teaspoons.

- b. Secondary outcome variables.

Our secondary outcome will be change in intake in added sugars among Peer Educators using the NHIS 5-factor screener. We will also examine change in cognitive restraint related to intake of foods high in added sugars using elements modified from the Three-Factor Eating Questionnaire R18. We will also examine weight change both Sidekicks and Peer Educators.

c. Statistical plan including sample size justification and interim data analysis.

We will conduct descriptive analyses comparing pre- and post-intervention. We will examine feasibility and acceptability outcomes with t-tests and Chi Square tests. We will compare the values of the Sidekicks' intake of added sugars before and after intervention with a paired, two-tailed ttests. We will use paired, two-tailed t-tests to compare Peer Educators' intake of added sugars, Sidekicks' weight, and Peer Educators' weight before and after the intervention. If our outcomes are not normally distributed, then we will use Wilcoxon signed-rank tests in lieu of t-tests.

d. Early stopping rules.

Not applicable

8. Risks

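### Does the 16.1 tsp/day detectable effect need restating because the pre-post correlation and the number of completers are not given?

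*Combined protocol and SAP*

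**What the plan says.** The only power statement is in section 7a: "With a sample size of 24, the minimal detectable intervention effect is reduction of added sugar intake by 16.1 tsp per day". Its stated conditions are "assuming a type I error of $\alpha=0.05$ (two-tailed), 80% power" and "assuming SD of outcome of 19 based on our prior survey". The same section defines the endpoint: "Our effect outcome will be change in intake in added sugars among Sidekicks". Section 7c plans to compare Sidekicks' "intake of added sugars before and after intervention with a paired, two-tailed ttests", with a Wilcoxon signed-rank test if the data are not normal.

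Three other places bear on the inputs.

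- Section 4a sets recruitment at 24 Peer Educators and 24 Sidekicks, so the 24 in the power statement equals the full Sidekick target.
- Section 3 (Preliminary Work) describes the source of the SD: "We completed a cross-sectional survey characterizing the personal diet".
- Section 7a treats retention as something to be measured: "Our feasibility outcomes will include recruitment and retention rates". Section 8b allows withdrawal at any time.

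No section gives a pre-post correlation, an SD of change, an assumed retention rate or an expected number of completers.

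**The concern.** A paired t-test works on within-person differences. Its detectable effect is set by the SD of those differences and by the number of people measured twice. The power sentence gives an SD of the outcome and a sample size, and labels neither in those terms.

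The SD is the more awkward of the two. The effect outcome is a change, so a literal reader could take 19 as the SD of change. That reading gives 11.35 tsp/day at 24 pairs, well short of 16.1, and the figure then looks wrong. If 19 is instead a single-visit SD, the figure implies zero correlation between two measurements on the same person, together with complete follow-up in a study that sets out to measure retention.

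Interpretation would be at stake. Section 7a follows the detectable effect with a scale: "a 12 oz can of soda has approximately 10 teaspoons of added sugars and a 20 oz bottle has approximately 17 teaspoons". A reader may conclude that the study can detect roughly a bottle a day but not a can, and that conclusion moves with the unstated inputs. With 24 pairs, power for a 10 tsp change is 42% at zero correlation and 89% at an assumed 0.7. At zero correlation, power for a 17 tsp change is 84% with 24 pairs and 74% with an assumed 19.

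**Working it through.** **Inputs from the protocol.** Two-sided alpha 0.05, power 80%, n = 24, SD 19 (section 7a); paired t-test (section 7c); cross-sectional source survey (section 3).

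**Inputs not in the protocol.** The pre-post correlation ρ and the number of completers. Any value used for them below is an assumption.

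**Formulae.** With a single-visit SD of 19 at both visits, SD of change = 19 × √(2(1 − ρ)). The minimal detectable effect is k × SD of change / √n. Here k is the noncentrality at which a two-sided 5% t-test on n − 1 degrees of freedom has 80% power; k = 2.926 for n = 24 and 2.954 for n = 20.

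**Step 1: reproduce the plan's figure.** Take n = 24 and ρ = 0.
- SD of change = 19 × √2 = 26.87.
- Standard error = 26.87 / √24 = 5.485.
- Detectable effect = 2.926 × 5.485 = 16.05 tsp/day.
- Power at 16.1 = 80.3%.

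The small gap between 16.05 and 16.1 disappears if the standardised effect (16.05 / 26.87 = 0.597) was rounded to 0.60, since 0.60 × 26.87 = 16.12.

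**Step 2: try other routes to 16.1.**

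| Calculation, SD 19 | Detectable effect (tsp/day) |
|---|---|
| Paired t, 24 pairs, ρ = 0 | 16.05 |
| Two-sample t, 24 v 24 | 15.70 |
| Normal approximation, ρ = 0 | 15.37 |
| Paired t, 24 pairs, 19 taken as SD of change | 11.35 |

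The paired t-test with ρ = 0 is the closest match, and it is the test that section 7c plans. Solving for ρ at n = 24 and an effect of 16.1 gives −0.007. At the stated size, then, a single correlation fits, and it is zero for practical purposes.

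**Step 3: what 19 can be.** A cross-sectional survey measures each person once, so it cannot supply an SD of change. The source of the SD and the match in step 1 both point to a single-visit SD.

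**Step 4: sensitivity to the unstated inputs.**

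| Completers | ρ = 0 | ρ = 0.3 | ρ = 0.5 | ρ = 0.7 |
|---|---|---|---|---|
| 24 | 16.05 | 13.43 | 11.35 | 8.79 |
| 20 (assumed) | 17.75 | 14.85 | 12.55 | 9.72 |

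The two omissions pull in opposite directions. A positive correlation brings the detectable effect below 16.1, and losses raise it. With 20 completers, ρ of about 0.18 brings it back to 16.1.

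**The case for a change.** The strongest case for a change is that this is the plan's only power statement, that estimating the likely effect is among the primary aims (section 4a), and that the fix would be one sentence. Having published a detectable effect with its alpha, power and SD, the protocol could fairly be expected to complete the list. Different pairs of inputs also give the same 16.1: 22 completers with a correlation of 0.09, 20 with 0.18, or 19 with 0.22. On that view a reader cannot know what was assumed, nor whether the figure is cautious or optimistic for the study as it will run.

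Part of this stands. The correlation and the allowance for loss are not stated, the 24 is not labelled as enrolled or completing, and the net direction of the two omissions cannot be settled from the documents.

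The claim that the assumption cannot be known does not stand. Each alternative pair replaces the stated 24 with a count that appears nowhere in the protocol. Held to its own n and its own test, the sentence has one solution. The can and bottle figures are offered as a scale for the reader; the plan does not make 10 or 17 tsp a target or a success threshold. Power against those values therefore shows sensitivity to assumed inputs and does not measure an error.

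**Conclusion.** No change to the plan is needed. The detectable effect is correct for its stated 24, taken as 24 complete pairs with a single-visit SD of 19 and zero pre-post correlation: 16.05 against a printed 16.1. What is missing is a description of those assumptions, and a statistician can recover them from sections 3, 7a and 7c.

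Nothing depends on the figure. The documents do not show that 24 was derived from it, section 7 attaches no progression rule or interim look to it, and the feasibility and acceptability outcomes do not use it. The paired test will use the SD of change actually observed and the Sidekicks actually followed up, so the estimate, its precision and the conclusion are the same whatever was assumed at planning.

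This rests on reading 19 as a single-visit SD, which the cross-sectional source and the reproduced figure both support. Anyone quoting 16.1 later should bear in mind that it makes no allowance for loss. With an assumed 20 completers and zero correlation it would be 17.75, while a modest positive correlation of about 0.18 would offset that loss.

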There is a risk of the loss of confidentiality of medical information. We will ensure protection of the data and any personal health information. Only the study team will have access to patient’s identifying information. Each participant will be assigned an identification (ID) number at the time of recruitment. The database that links the ID with the participant will only be accessible by the principal investigator. Data will be stored on the Johns Hopkins Department of Medicine Network Drive, which is password- protected and backed-up each night. If a participant changes his/her mind and does not wish to complete the study s/he may withdraw at any point.

There is a risk of potential stress, discomfort, boredom or inconvenience from answering survey questions and undergoing biometric measurements. Participants will be informed that they do not have to answer any questions that they do not wish or have their blood pressure, height, or weight measured.

There are risks related to interview location. Interviews will occur either at the public housing developments’ administrative buildings or in the participant’s home, depending upon participant preference.

Interviews in the administrative or community building(s). To ensure participants’ privacy, we will conduct interviews in a private room or private screened booth in a conference room. We will play background music to decrease risk of others overhearing the interviews.

Interviews in the participant’s home. To ensure the safety of our research assistants during data collection, we will require two data collectors to attend all home interviews. Research assistants will also be trained in safety procedures, and will be encouraged to halt interviews if they have concerns for their personal safety. There is also the potential for a member of our research team to encounter a potential emergency situation that is not related to study participation (e.g., dehydration, environmental risk, medical emergency). We refer to such events as “alerts” and have procedures for their management, which are outlined in Table 2.

Table 2. Proposed algorithm for home emergencies	
Alert	Action

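### On its natural reading, the paired test in section 7c drops every Sidekick without a 6-month value and leaves 3-month intake unused, so selective loss would bias the estimated change in either direction.

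*Combined protocol and SAP*

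**What the plan says.** The effect outcome in section 7a is the change in Sidekicks' added-sugar intake on the NHIS screener. Section 4a makes this estimate part of the primary purpose: the pilot is to test acceptability and feasibility "as well as estimate the likely effect of the intervention".

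Section 7c analyses Sidekicks' "intake of added sugars before and after intervention with a paired, two-tailed ttests", with a Wilcoxon signed-rank test if the data are not normal. It does not name the after visit, define an analysis set or give a rule for missing values.

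Other sections bear on this:

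- **Timing (4a).** Six weekly core sessions are followed by "3 additional booster sessions over the subsequent 3 months after completing the core curriculum".
- **3-month intake (4a).** The individual-level questions include "Dietary content with brief food frequency questionnaire using the 5-Factor NHIS screener". The same section adds: "At 3 months, an abbreviated survey will be conducted that includes only individual-level questions, biometric measurements, and satisfaction with the intervention". Sidekick intake is therefore collected at baseline, 3 months and 6 months.
- **Loss (7a, 8b).** Retention is itself an outcome: "Our feasibility outcomes will include recruitment and retention rates, as well as program attendance". A participant who "does not wish to complete the study s/he may withdraw at any point", and individual questions may be declined.
- **Measures that limit loss (4a, 10).** Visits may take place in the administrative building "or during home visits based on participant preference". Each assessment is paid: $50, $25 and $50.

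**The concern.** A paired t-test and a signed-rank test both need two values per person. With 6 months as the after visit, a Sidekick seen at baseline and 3 months but not at 6 months contributes nothing. The estimate is then the mean change among those who stayed, and it equals the mean change among all enrolled only if staying is unrelated to response.

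The direction is not known in advance. People who have not cut down may avoid the last visit, or people who have done well may see no need for it. Reporting retention shows how many were lost but does not correct the estimate. The estimate is what this pilot is meant to deliver, and with 24 Sidekicks each loss is about 4% of the sample.

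**Working it through.** **The plan's own figure.** Section 7a gives a minimal detectable reduction of 16.1 tsp/day for n = 24, SD 19, two-sided alpha 0.05 and 80% power. A paired t-test on 24 pairs, with SD of change 19 × √2 = 26.87 (zero correlation between visits), gives 16.05 by the noncentral t, and power at 16.1 is 80.3%. The figure is therefore reproduced with all 24 pairs complete. It contains no allowance for loss.

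**Which visit is the after visit.** Six weeks plus 3 months is about 4.5 months if sessions start at baseline. The 3-month visit falls during the boosters, and only the 6-month visit follows the intervention.

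**Bias by identity (no model needed).**

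Completers' mean − mean of all 24 = (number lost / 24) × (mean change in retained − mean change in lost).

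| Assumed difference | 2 lost | 4 lost | 6 lost |
|---|---|---|---|
| 10 tsp/day (one 12 oz can, section 7a) | 2/24 × 10 = 0.8 | 4/24 × 10 = 1.7 | 6/24 × 10 = 2.5 |
| 5 tsp/day | 0.4 | 0.8 | 1.3 |

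**Simulation.** From the documents: n = 24 and SD 19. Assumed: equal correlation ρ between visits, true change −5 tsp/day, and 24% lost before 6 months, after the 3-month visit unless stated. The log-odds of loss rise by 1 per 19 tsp of 3-month change. At ρ = 0.5 this means about 8% lost among those one SD better than average and 41% among those one SD worse. There were 40,000 trials per setting. The all-visit estimate is maximum likelihood with unstructured covariance.

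Mean estimated change (truth −5), completers v all-visit:

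| Loss mechanism | ρ = 0.3 | ρ = 0.5 | ρ = 0.7 |
|---|---|---|---|
| Random | −5.0 v −5.0 | −5.0 v −5.0 | −5.0 v −5.0 |
| 3-month change, slope 1 | −7.6 v −5.0 | −6.9 v −5.0 | −6.3 v −5.0 |
| 3-month change, slope 0.5 | −6.5 v −5.0 | −6.1 v −5.0 | −5.7 v −5.0 |
| 3-month change, slope −1 | −2.4 v −5.0 | −3.1 v −5.0 | −3.8 v −5.0 |
| Unseen 6-month change, slope 1 | −10.1 v −8.3 | −8.9 v −7.7 | −7.5 v −6.8 |
| Slope 1, all loss before 3 months | −7.6 v −5.9 | −6.9 v −6.0 | −6.3 v −5.9 |

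At slope 1 on 3-month change the completers' bias is 2.6 / 1.9 / 1.3 tsp/day. Against empirical standard errors of 5.21 / 4.37 / 3.43, that is 0.4 to 0.5 of a standard error.

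With no true change, the planned t-test rejects in 7.7% / 7.1% / 6.3% of trials at slope 1 and in 5.8% / 5.6% / 5.4% at slope 0.5, against a nominal 5%. The Wilcoxon test gives 7.2% / 7.2% / 5.7% at slope 1 (4,000 trials).

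With skewed (gamma) intake, slope 1 gives a similar pattern: −7.1 / −6.7 / −6.2 for completers v −4.8 / −4.8 / −4.9.

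**The case against.** **The fault is inferred.** Section 7c does not say that incomplete pairs will be dropped, nor that 6 months is the after visit. That follows from the session timetable and from what a paired test needs. The 3-month form is abbreviated and its appendix is not in the document, so the screener's presence rests on section 4a alone. This is fair, but no other section gives a different rule and the reading is the natural one.

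**Every input to the bias is assumed.** The documents give no dropout rate, mechanism or correlation between visits, and a slope of 1 is steep. Sidekicks have no sessions to attend, may be seen at home and are paid for visits. Loss may simply reflect moving or lost contact, and then there is no bias. This stands, so the sizes above are a range and not a forecast.

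**The gain is modest.** At ρ = 0.5, root mean squared error (completers v all-visit) is 4.81 v 4.44 at slope 1, 4.52 v 4.31 at slope 0.5, and 4.09 v 4.02 if only 2 of 24 are lost. The confidence interval will be about 9 tsp/day either side in any case. In a single-arm pilot the error-rate argument carries little weight. This also stands.

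**The correction is partial where informative loss is most worrying.** If loss depends on unseen 6-month change, 2.7 of 3.9 tsp/day of bias remains at ρ = 0.5. If all loss precedes 3 months, 1.0 of 1.9 remains. In addition, the simulation did not test convergence at n = 24, a fallback covariance, or visits missed intermittently. These limits argue for keeping the planned test beside the model. They do not argue for discarding the 3-month data.

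**Conclusion.** The concern holds, as an inexpensive improvement rather than a serious fault. With 6 months as the after visit, the planned test uses complete pairs only and gives collected 3-month intake no role. If loss is related to response, the estimate is biased in a direction that cannot be known beforehand.

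Plausible sizes are 0.4 to 2.5 tsp/day by the identity, for 2 to 6 lost and a 5 to 10 tsp/day difference. In the simulations they are 0.7 to 2.6 when loss follows 3-month change, and up to 5.1 when it follows unseen 6-month change. All rest on assumed loss; under random loss the bias is zero. An all-visit model removes the bias to within 0.1 tsp/day when loss after 3 months depends on the observed 3-month change, and reduces it otherwise.

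**What to change.** In section 7c:

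1. Name 6 months as the after visit.
2. Estimate the baseline-to-6-month change, with a 95% confidence interval, from a likelihood-based repeated-measures model on all enrolled Sidekicks. Use baseline, 3 and 6 months, visit as a factor, unstructured covariance (compound symmetry if that does not converge) and small-sample degrees of freedom.
3. Keep the paired t-test, with its Wilcoxon fallback, on complete pairs alongside.
4. Report the number of pairs and the 3-month change among those lost, so that the likely direction of bias can be seen.

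Setting a missing 6-month value to baseline is optional and only a cautious check. Under random loss of 24% it turns a true −5 into 0.76 × −5 = −3.8, so it should not be read as a second estimate.

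**Cost.** A little more analysis and no new data, visits or participants. Precision does not improve (standard error 4.4 v 4.4 tsp/day at ρ = 0.5). The model assumes that loss depends only on observed intake, and the report should say so.
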